Methods: Linear Statistical Models will be fit containing parameters for the main effect of each stimulation setting (Vol, CV, and Stand) and additive effects of weight bearing stand training for each stimulation setting. This hypothesis will be tested using the stand training coefficient corresponding to CV-scES. See section G for more details.

Specific Aim 3:

Understand the effects of scES alone and scES with stand training on respiratory, bladder, bowel and sexual function.

Secondary Analyses:

Hypothesis 3a: CV-scES selected for cardiovascular function will result in greater improvements in respiratory, bladder, bowel and sexual function than Vol-scES selected for voluntary movement

Rationale: We propose that CV-scES will further activate spinal autonomic circuitry and thus influence similar systems, respiratory, bladder, bowel and sexual function in addition to these mechanisms occurring with improvements in the cardiovascular system.

Methods: Linear Statistical Models will be fit containing parameters for the main effect of each stimulation setting (Vol, CV, and Stand) and additive effects of weight bearing stand training for each stimulation setting. This hypothesis will be tested using the contrasts between the stimulation settings both with and without weight bearing stand training. See Section G for more details.

Hypothesis 3b. CV-scES selected for cardiovascular function combined with task specific stand training using Stand-scES will result in greater improvement in respiratory, bladder, bowel and sexual function than CV-scES alone.

Rationale: Exercise programs involving limb muscles are known to increase fitness and improve ventilatory function in individuals with chronic SCI [81, 82]. However, none of the respiratory rehabilitative modalities have yet been proven to be clinically effective in patients with chronic SCI [83]. Preliminary results of locomotor training studies from our center indicate that the weight bearing step training in individuals with motor complete SCI leads to increased spinal motor output to respiratory muscles, but does not improve the voluntary initiated respiratory muscle activating patterns [84]. We have also found that weight-bearing exercise improves bladder function. Thus the combination of CV-scES with scES stand training will provide the greatest effect.

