Methods: Linear Statistical Models will be fit containing parameters for the main effect of each stimulation setting (Vol, CV, and Stand) and additive effects of weight bearing stand training for each stimulation setting. This hypothesis will be tested using the contrasts between the stimulation settings both with and without weight bearing stand training. See Section G for more details.

Specific Aim 4.

Measure impact of scES and training on quality of life.

Secondary Analyses:

Hypothesis 4a: Quality of Life will significantly improve with scES.

Rationale: Loss of movement results in reduced mobility and less access to the community and employment, significantly affecting individuals with SCI. They may also have low systolic blood pressure compared to uninjured or paraplegic patients [6]. These cardiovascular changes may contribute to poorer reporting of measures of general health, increased fatigue, cognitive deficits, impaired social well-being, and depression [85-92], leading to a decreased quality of life. We will administer quality of life measures to assess the impact of scES and training on these individuals' quality of life. We will use Spinal Cord Functional Index (version 1), selected scales from the Spinal Cord Injury-Quality of Life (SCI-QOL) measurement system and the EuroQoL 5-Dimensional 3 Level Scale (EQ-5D-3L). The SCI-QOL measurement system employs a computerized adaptive testing (CAT) approach to provide a reliable, valid and practical means for multi-dimensional quality of life assessment. The SCI-FI and SCI-QOL build on the work of the Patient Reported Outcomes Measurement Information System (PROMIS) and the Neurology Quality of Life Initiative (Neuro-QOL). Classical and contemporary test development methodologies were employed to develop the SCI-QOL.

Qualitative input was obtained from individuals with SCI and clinicians through interviews, focus groups, and cognitive debriefing. Item pools were field tested in a multisite sample (n=877) and calibrated using 2-parameter item response theory methods. Initial reliability and validity testing was performed in a new sample of individuals with traumatic spinal cord injury [93-95]. The SCI-QOL is a validated, reliable measurement

system consisting of psychometrically sound measures for individuals with SCI. The SCI-QOL also links to other measures designed for a general medical population.

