For those participants not achieving independent standing during the stand training phase of the protocol, the home and community integration will include training in a customized standing device. Standing devices will be designed to match the level of assistance required to safely translate the training to the home environment. This phase can also include training of care givers or personal trainers to assist the participants in achieving safe and independent standing.

G. Statistical approaches.

For the primary aims (comparing to baseline), paired sample t-tests will be used the primary endpoints (hypotheses 1a, 1b, 1c) comparing the results at the end of the second intervention period to the baseline period.

For the secondary aims, each endpoint will be analyzed separately with a common linear model framework. We fit a linear model with effects for each stimulation setting (voluntary, cardiovascular, and standing) and an effect of weight bearing stand training within each stimulation setting. Thus, for example we have a coefficient which measures the additional benefit of weight bearing stand training and a stimulation setting over and above that stimulation setting alone. There are separate coefficients for the benefit of stand training within Vol-scES, CV-scES, and Stand-scES. Formally, we fit a linear model of the form

$$\begin{aligned} \text{Response} = & \beta_{\text{Vol-scES}} I_{\text{Vol-scES}} + \beta_{\text{CV-scES}} I_{\text{CV-scES}} + \beta_{\text{Stand-scES}} I_{\text{Stand-scES}} + \\ & \beta_{\text{VT}} I_{\text{Vol-scES and Training}} + \beta_{\text{CVT}} I_{\text{CV-scES and training}} + \\ & \beta_{\text{ST}} I_{\text{Stand-scES and training}} + \text{error} \end{aligned}$$

where the β terms give the regression coefficients and I_X is an indicator variable equal to 1 if X occurs and 0 otherwise. The indicator variables function to only include the coefficients of the model for treatments the participant actually receives. Thus, for a participant receiving CV-scES and stand training, the model would reduce to

$$\text{Response} = \beta_{\text{CV-scES}} + \beta_{\text{CVT}} + \text{error}$$

Due to the partial crossover, no carryover effects are included in the model (sensitivity analyses using only the first period data will also be summarized). Random effects for each subject may be included when appropriate.

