For hypotheses related to differences between the stimulation settings (hypotheses 1d, 1e, 1f, 3a, 3b), contrasts between the stimulation parameters will be used to test the hypothesis. For example, to test the superiority of CV-scES to the other two settings, the contrasts $\beta_{\text{CV-scES}} - \beta_{\text{Vol-scES}}$ and $\beta_{\text{CV-scES}} - \beta_{\text{Stand-scES}}$ will be used (testing if the difference is greater than 0) if interest centers on stimulation alone, and the contrasts $\beta_{\text{CV-scES}} + \beta_{\text{CVT}} - \beta_{\text{Vol-scES}} - \beta_{\text{VT}}$ and $\beta_{\text{CV-scES}} + \beta_{\text{CVT}} - \beta_{\text{Stand-scES}} - \beta_{\text{ST}}$ if interest centers on stimulation with stand training.

For hypotheses related to the effect of stand training above and beyond stimulation only, the parameters, β_{VT} , β_{CVT} , and β_{ST} may be tested directly (for hypotheses 2a, 2b, 2c)

Comparisons between stimulation frequencies have 90% power to detect effect sizes of 1.7 or higher with size 0.05 (one-sided) tests.

H. Uniqueness of initiative. The present proposal is designed to determine the effectiveness of a novel intervention on the recovery of multiple physiological systems after complete paralysis. There is no current intervention with demonstrated effectiveness in the recovery of motor or autonomic function after complete paralysis except via epidural spinal cord stimulation. The intervention of epidural stimulation applied with our newly developed stimulation parameters is based on a fundamentally sound neurophysiological concept: that the spinal circuitry can be neuromodulated to a physiological state with modest levels of epidural stimulation whereby proprioception itself can contribute to the recovery of the ability to stand and voluntarily control movement below the level of injury. Our experimental strategy embraces a completely new philosophy where the objective is to understand how multiple systems that are normally highly integrated and interdependent respond as such after a severe spinal cord injury, and to establish the efficacy of ES in regaining the ability to:

1. improve cardiovascular function,
2. volitionally control movement,
3. stand independently
4. improve bowel and bladder function,
5. improve sexual function
6. improve respiratory function,
7. improve quality of life, and
8. reduce health care costs.

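### Hypothesis 3b asks whether stand training adds to CV-scES, but the protocol tests it with contrasts between stimulation settings, which answer a different question

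*Protocol*

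**What the plan says.** Under Specific Aim 3 (Protocol, Section III.C), hypothesis 3b is that CV-scES "combined with task specific stand training using Stand-scES will result in greater improvement in respiratory, bladder, bowel and sexual function than CV-scES alone". Its Methods paragraph then states: "This hypothesis will be tested using the contrasts between the stimulation settings both with and without weight bearing stand training". The same sentence stands under hypothesis 3a, which compares CV-scES with Vol-scES.

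Section III.G fits one linear model to each secondary endpoint. It has an effect for each stimulation setting and a training effect nested in each setting: "There are separate coefficients for the benefit of stand training within Vol-scES, CV-scES, and Stand-scES". It then assigns tests to hypotheses in two groups:

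- Between-setting group: "For hypotheses related to differences between the stimulation settings (hypotheses 1d, 1e, 1f, 3a, 3b), contrasts between the stimulation parameters will be used". The contrasts written out are CV minus Vol and CV minus Stand, first for stimulation alone and then with training added on both sides.
- Training group: the three training coefficients "may be tested directly (for hypotheses 2a, 2b, 2c"). Hypothesis 3b is not listed, and Specific Aim 2 contains only 2a and 2b.

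Hypothesis 2b makes the same comparison as 3b, on cardiovascular outcomes. Its Methods paragraph says: "This hypothesis will be tested using the stand training coefficient corresponding to CV-scES".

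**The concern.** The question in 3b holds the stimulation setting constant and varies training. The assigned test holds training constant and varies the stimulation setting. These are different parameters, and either can be zero while the other is large.

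The error can run in both directions. A real benefit of stand training on respiratory, bladder, bowel or sexual function could go undetected, or such a benefit could be claimed when only the choice of stimulation setting matters. The Specific Aims text names the need for stand training, for these outcomes among others, as something the trial is meant to determine. An analysis plan that followed the protocol would inherit the mismatch. One that departed from it could look like a post hoc change of test.

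**Working it through.** **Notation.** Write V, C and S for the effects of Vol-, CV- and Stand-scES, and VT, CVT and ST for the training effects within each (Section III.G).

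**1. What 3b asks.** The mean with CV-scES and training is C + CVT. The mean with CV-scES alone is C. The difference is (C + CVT) − C = CVT.

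**2. What Section III.G assigns.** The four contrasts are:

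- C − V
- C − S
- (C + CVT) − (V + VT)
- (C + CVT) − (S + ST)

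As vectors in the six coefficients they have rank 4. Adding CVT as a fifth row raises the rank to 5, so no linear combination of the four equals CVT. Subtracting the first from the third gives CVT − VT, an interaction, which is not 3b either.

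**3. Two cases that show the mismatch.**

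| True effects | All four contrasts | CVT |
|---|---|---|
| Training adds 1 in every setting; settings equal | 0 | 1 |
| CV better by 1 than the other settings; training adds nothing | 1 | 0 |

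**4. The protocol's own figure.** The only figure attached to this family of contrasts is: "Comparisons between stimulation frequencies have 90% power to detect effect sizes of 1.7 or higher with size 0.05 (one-sided) tests". With the normal approximation, power is Φ(d√(n/2) − 1.645). At d = 1.7 and n = 6 per group this is Φ(2.944 − 1.645) = 90.3%, so the figure reproduces with the 6 per group given in Section III.B. With the 9 per group in Table 1 it is Φ(3.606 − 1.645) = 97.5%. That discrepancy is a separate matter, and the present point does not depend on it.

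**5. Size of the consequence.** The protocol gives no SD or expected effect for the Aim 3 outcomes, so the effects below are assumptions. The calculation is a two-sample t test of CV against Vol with 9 per group (Table 1), first-period data, one-sided 0.05, noncentrality d√(9/2) and 16 df.

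| CV minus Vol, no training effect | Probability that the assigned test supports 3b |
|---|---|
| 0.5 SD | 26.5% |
| 1.0 SD | 65.0% |
| 1.45 SD | 90.3% |

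In the opposite case (training adds the same amount to CV and Vol, settings equal), the noncentrality is zero and each test rejects 5% of the time whatever the benefit.

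The two tests can be put side by side with four cells of 9, pooled 32 df and an assumed effect of 1.7 SD:

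| True effects | CV-versus-Vol contrasts | Test of CVT |
|---|---|---|
| Training adds 1.7 SD in both settings; settings equal | 5.0% | 97.0% |
| CV exceeds Vol by 1.7 SD; training adds nothing | 97.0% | 5.0% |

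**6. Using both periods.** Section III.G treats first-period-only analysis as a sensitivity analysis. With both periods in the model (generalised least squares, 9 per arm, within-subject correlation 0 to 0.7, normal approximation), a 1.0 SD advantage of CV over Vol with no training effect gives rejection rates of 68% to 80% for the stimulation-alone contrast and 93% to 98% for the with-training contrast. The first-period figure of 65% is therefore the milder illustration.

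**The case against.** The strongest reply is that Section III.G already contains the correct rule in general terms. It says that hypotheses about what training adds to stimulation may be tested by the training coefficients, and 3b belongs there by content. The model estimates β_CVT for every secondary endpoint, and the written contrasts are introduced only as an example. On this view the fault is a misplaced label plus text carried over from 3a.

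That explains how the error may have arisen but does not remove it. The rule comes with an explicit list that leaves 3b out, 3b is named in the other list, and its own Methods paragraph repeats the wrong test. The phrase there about being with and without training might be read as a training comparison, but Section III.G spells it out as comparisons between settings at each training status.

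Four qualifications stand:

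- The percentages rest on assumed effects and on 9 per group. With the 6 per group given in Section III.B, the 65% at 1.0 SD becomes 49%.
- The 5% applies to a single contrast. Section III.G names two per question and does not say whether one or both must succeed. With two contrasts sharing the CV estimate (correlation 0.5 assumed), the rate would be about 9% if either suffices and about 1% if both are required.
- β_CVT is the right parameter but not a clean one in the two-period model. Group A receives training only in the second period, and the model has no period or carryover term, so the coefficient also absorbs time and accumulated stimulation.
- What 2c was meant to be cannot be told from the document.

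**Conclusion.** The concern holds. The protocol assigns 3b a test of a different parameter, in two places, and treats the structurally identical 2b correctly. The conclusion follows from the protocol's own model and needs no assumption about effect sizes.

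The size is illustrative. When training helps CV-scES and Vol-scES equally and the settings do not differ, each CV-versus-Vol test has no power beyond its 5% level. When training does nothing and CV-scES exceeds Vol-scES by an assumed 1.0 SD, it supports 3b about 65% of the time with 9 per group in the first period, and more often with both periods. The reach is limited to one secondary hypothesis across four outcome domains; hypotheses 1a to 1c are not affected. It should be corrected before analysis.

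**What to change.** In Section III.G, take 3b out of the between-setting list and add it to the list for the training coefficients, stating that it is tested by β_CVT > 0. That list should then read 2a, 2b, 3b. Delete 2c after the sponsor confirms that no such hypothesis is intended; if one is, state it under Specific Aim 2. Replace the test sentence in the 3b Methods paragraph with the one used for 2b.

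The change costs only wording: no extra data, participants or model terms. It does not remove the confounding of training with period in Group A. The first-period sensitivity analysis already planned, which for this hypothesis compares randomised arms B2 and A2, should therefore be reported beside the main estimate for 3b.

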Procedure: Participants will participate in laboratory sessions until all optimal configurations for joint movement and trunk control are found. Participant will demonstrate safe use of the patient programmer and ability to perform the leg voluntary movement independently or in the presence of a care giver. This will take approximately 3–5 days. Once the participant has demonstrated safe use of programs they will be allowed to conduct the sessions at home. Participants will be asked to train daily (7 days a week) for a total of 80 sessions.

Participants in the Voluntary-scES group (A1) will receive Core voluntary training focusing on trunk exercises, sitting balance, and lower extremity training for 6 hours daily. Voluntary training will be performed in the laboratory under supervision of trained research staff until they can perform each task safely and independently. Then they will be able to conduct their training at home. Approximately every two weeks, lower extremity voluntary configurations will be assessed by research staff to make sure they are still optimized for the desired movement. They may train in the laboratory more often.

3. Cardiovascular Intervention.

Participants will undergo testing in the laboratory to determine the optimal stimulator configuration(s) for blood pressure regulation. The first 5 training sessions will be performed in the laboratory. Once 3 consecutive stable days are achieved with the same stimulation parameters and the participant has demonstrated safe use

of the programmer, they will be sent home for one day to perform the stimulation at home. The participant will return to the laboratory the following day for stimulation with blood pressure monitoring. Provided cardiovascular parameters remain stable, the participant will be allowed to train at home for 3 days prior to returning to the laboratory for stimulation with monitoring. If cardiovascular parameters remain stable, the participant will be able to begin the home training program of 6 days a week and 1 day in lab training. Participants will be asked to train with CV-scES for CV for approximately 6 hours daily (7 days a week) for a total of 80 CV training sessions. Participants are instructed to monitor blood pressure for at least 15 minutes prior to starting CV-scES each day in order to insure a stable baseline prior to starting stimulation.

4. Stand Intervention.

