No individual will be allowed to participate in the study without being examined by the study physicians. All eligible research participants will be encouraged to discuss the study with their primary physician, in order to minimize physical risks. Participants will be continuously monitored for any signs of discomfort or risks by a designated research staff member during every assessment and intervention. The skin integrity will be checked and the joints will be examined for swelling or redness after every assessment and training session. Blood pressure and heart rate will be routinely measured. If discomfort or any risks persist, the recording or training session will be immediately discontinued and the research nurse will be contacted immediately to assess the participant. If needed the study physician or physician assistant will be notified and will also examine the individual. Immediate medical care will be provided when necessary. Their primary care provider will be informed when necessary. If there are no medical events during the intervention or assessment this will be noted and verified with a signature by a research team member.

Before and after every experiment and training session, a physical therapist or activity based technician will examine the subject's skin for irritations and abrasions. If skin irritations or abrasions are caused by the recording or stimulating electrodes, or hand placements of trainers, electrode and hand placement will be modified appropriately. Further, the physical therapist or activity based technician will constantly monitor the subject's skin and muscle for signs of muscle strain, joint sprain and skin irritation (e.g. temperature and redness).

Each participant will be assigned an observer to accompany the research participant to experiments and training sessions. The responsibility of the observer is to communicate with the research participant and monitor their well-being. The observer, the activity based technicians, the research nurse and/or the research physical therapist will monitor the research participant daily for skin redness, swelling of joints or spasticity as well as other issues. Adverse events will be reported as required by the institutional review board. The assigned observer may be either a University of Louisville Employee or a KentuckyOne Health Employee.

b. Epidural Stimulation: Electrode Configuration, Assessments and Interventions

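### The protocol promises staff monitoring, skin checks and a sign-off for every session, yet sends most CV-scES and Vol-scES sessions home, where no blood pressure reading is set during CV-scES

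*Protocol*

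**What the plan says.** Section IV.C.2.a (General protection against risk) makes its promises without exception. On monitoring: "Participants will be continuously monitored for any signs of discomfort or risks by a designated research staff member during every assessment and intervention". On skin: "Before and after every experiment and training session, a physical therapist or activity based technician will examine" the participant's skin. If no medical event occurs during an intervention or assessment, "this will be noted and verified with a signature by a research team member". Each participant also has an assigned observer who goes along to experiments and training sessions. On vital signs it says only: "Blood pressure and heart rate will be routinely measured".

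Section III.E then moves two of the interventions out of the laboratory.

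- **Vol-scES (III.E.2):** "Voluntary training will be performed in the laboratory under supervision of trained research staff until they can perform each task safely and independently"; after that, training is at home. Staff reassess leg configurations about every two weeks, and "They may train in the laboratory more often".
- **CV-scES (III.E.3):** the first five sessions are in the laboratory. After three consecutive stable days on the same parameters and demonstrated safe use of the programmer, there is one home day, a laboratory day, three home days and a laboratory return. If all is stable, "the participant will be able to begin the home training program of 6 days a week and 1 day in lab training". Sessions last about 6 hours. The home blood pressure instruction is: "Participants are instructed to monitor blood pressure for at least 15 minutes prior to starting CV-scES each day".

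Section IV.C.2.b (Epidural Stimulation) deals with laboratory and home use separately. Close blood pressure and heart rate monitoring throughout stimulation is stated for laboratory sessions, followed directly by a rule to stop when those values become abnormal or certain symptoms appear. For home use it restricts programs to those tested in the laboratory, tells participants to call at once if a complication develops, and returns them to the laboratory for at least a week after a stimulation-related serious adverse event.

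**The concern.** The general protection section is where an ethics committee or monitoring board looks to see how participants are watched. As written, it describes a level of supervision that the intervention sections do not provide for sessions conducted at home. Staff cannot watch, examine or sign for a session that a participant runs alone or with a caregiver.

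The matter is more than tidiness for CV-scES. That stimulation is meant to change blood pressure, and inclusion criterion 7 (IV.A) selects people for cardiovascular dysfunction such as persistent low pressure, autonomic dysreflexia or orthostatic hypotension. A change that produces symptoms would prompt a call. A change without symptoms during a home session would be noticed only if someone happened to take a reading, and the protocol does not set one for that time.

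**Working it through.** The protocol gives no count of home sessions, so there is no stated figure to reproduce. The check has three parts.

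**1. How many sessions may be at home?**

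*CV-scES.* Inputs from III.E.3: 80 sessions; a laboratory lead-in of L sessions (at least 5); then 1 home, 1 laboratory, 3 home, 1 laboratory; then a repeating week of 6 home and 1 laboratory.

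- With L = 5, the lead-in and staged release take 5 + 6 = 11 sessions, 4 of them at home. The remaining 69 are nine full weeks (63 sessions, 54 at home) plus 6 home days: 54 + 6 = 60. Total at home: 4 + 60 = 64 of 80 (80%).
- With L = 10: 16 sessions used, 64 left = nine weeks plus 1 home day; 4 + 54 + 1 = 59 (74%).
- With L = 20: 26 used, 54 left = seven weeks plus 5 home days; 4 + 42 + 5 = 51 (64%).

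The lead-ins of 10 and 20 are assumptions, to show what slower stabilisation does.

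*Vol-scES.* III.E.2 gives about 3 to 5 days to find configurations and show safe use, daily training, 80 sessions, and a staff check about every two weeks. Two assumptions are needed: the 3 to 5 days count as sessions, and each check replaces a home session. There are 77/14 or 75/14, so about 5, checks.

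- 80 − 3 − 5 = 72 (90%) and 80 − 5 − 5 = 70 (88%).
- With an assumed lead-in of 10 (5 checks) or 20 (4 checks): 65 (81%) or 56 (70%).

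The 64 and the 70 to 72 are what the text permits at earliest release, not fixed counts. A majority of sessions at home holds across these ranges.

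**2. How much staff contact is there anyway?**

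Under Table 1, 36 participants × 2 periods = 72 participant-periods. Stand training, with trainers present 5 days a week (III.E.4), applies to Group B in both periods (18 × 2 = 36) and to Group A in the second (18). That is 54 of 72 (75%). Weekly (CV-scES) or roughly two-weekly (Vol-scES) contact is the scheduled minimum after home release only in the other 18, Group A in period 1.

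**3. Which blood pressure provisions reach a home CV-scES session while stimulation is on?**

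| Provision | Section | Reaches each home session during stimulation? |
|---|---|---|
| At least 15 minutes of monitoring | III.E.3 | No: before stimulation starts |
| Close monitoring throughout stimulation | IV.C.2.b | No: laboratory sessions |
| Stop if values become abnormal | IV.C.2.b | No: refers back to the laboratory readings |
| Modify or stop for pressure fluctuations or dizziness | IV.C.2.b | Not limited to the laboratory, but sets no reading or threshold |
| Routine measurement | IV.C.2.a | No home schedule |
| 24-hour ambulatory recording | III.D.2.a, Appendix 1 | Periodic and monthly only; analysed after completion |
| Call staff if a complication develops | IV.C.2.b | Yes, but depends on the participant noticing it |

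No row sets a reading, or a value at which to stop, during each home session of about 6 hours.

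**The case against.** The best defence is that IV.C.2.a is general text, plainly written with attended sessions in mind: it speaks of trainers' hand placements and an accompanying observer. The specific rules for home use are in III.E and IV.C.2.b, and staff following those would know what to do. Release to home CV-scES is staged and requires demonstrated stability, and most participant-periods bring trainers into contact five days a week. How often to measure at home is for the investigators to judge.

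Much of this stands. It shows that the conflict is mainly one of wording and that participants are far from unseen. It does not make the unqualified promises true, and stand training sessions do not put staff at home CV-scES or Vol-scES sessions.

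Three stronger readings are tempting, and the documents do not support them.

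- A reader might infer that the stop rule for abnormal values is a home rule with nothing to feed it. The values it names are those of the preceding sentence, which concerns laboratory sessions. It is a laboratory rule with a laboratory input; what is absent is a home counterpart.
- A reader might infer that home training has no safeguards. Those listed above are real, and IV.D adds a weekly medical event report.
- A reader might turn the risk category for blood pressure changes in cardiovascular training (IV.B) into a number of undetected home events. IV.B calls its categories general ranges, and they are not specific to home sessions or to missed events. Nor can the share of home sessions without any reading be calculated, because the number of periodic ambulatory recordings is not stated.

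**Conclusion.** The conflict is real. The monitoring, skin-check and sign-off statements in IV.C.2.a cannot be met for home sessions that III.E permits: up to 64 of 80 CV-scES sessions at earliest release, and roughly 70 to 72 of 80 Vol-scES sessions if set-up days count as sessions and checks replace home days. Slower release lowers both figures.

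The substantive gap is confined to CV-scES: the only blood pressure instruction set for each home session precedes stimulation, and no value-based stop is set for the hours that follow. I rate this a minor-to-moderate safety correction. The documents do not allow an estimate of how many events would be missed, and the sample size and analysis are untouched.

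**What to change.** Two changes.

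1. In IV.C.2.a, limit the monitoring, skin-check, observer and signature statements to supervised sessions, and cross-refer to III.E.2, III.E.3 and IV.C.2.b for home sessions.
2. In III.E.3, extend the home CV-scES instruction beyond the pre-stimulation check: at least one reading after stimulation starts and further readings during the session, with stop-and-call thresholds set by the investigators for each participant. Readings go in a short log that feeds the existing weekly medical event report.

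No matching check is proposed for home Vol-scES.

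The cost is protocol wording, a short log and a small daily burden on participants or caregivers. That burden is larger for people with impaired hand function, who already need a caregiver's help with the ambulatory monitoring diary. Participants are already told to monitor blood pressure before each CV-scES session, so new equipment should not be needed. The protection statement will promise less, but it will be accurate.
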